6.2 Sacituzumab Govitecan Packaging and Storage

All vials of study drug must be stored under refrigeration (monitored at 2-8°C) in a locked room that can be accessed only by the pharmacist, the study Investigator, or another duly designated person. The study medications must not be used outside of the context of this protocol. Under no circumstances should the Investigator or other site personnel supply study drug to other Investigators, subjects, or clinics, or allow supplies to be used other than directed by this protocol without prior authorization from Gilead Sciences, Inc..

6.3 Sacituzumab Govitecan Preparation and Administration

For subject dose preparation, Sacituzumab Govitecan is to be reconstituted with normal saline for use, and diluted immediately into infusion bags. Sacituzumab Govitecan is photosensitive and should be protected from light during storage and use per guidance provided below.

Appropriate use of aseptic technique should be employed in preparing the dose. Allow the Sacituzumab Govitecan vials to warm to room temperature to allow faster dissolution. The 200mg lyophilized powder in each vial should only be reconstituted using 20ml 0.9% sterile sodium chloride (normal saline). The reconstituted solution should be gently shaken and allowed to dissolve for up to 15 minutes. Calculate the prescribed dose in mg based on the subject's body weight at the beginning of EACH cycle, or more frequently if the subject experiences a weight change (increase or decrease) >10% at day 8 of the cycle. The appropriate calculated amount should then be withdrawn from the supplied vials of study medication. 21-gauge needle use is recommended. Inject the solution into a glass or plastic infusional container slowly to minimize foaming and do not shake the contents. Adjust the volume in the infusional container as needed with normal saline to obtain a concentration of 1.1-3.4 mg/mL (total volume should not exceed 500 mL). Only normal saline should be used since the stability of the reconstituted product has not been determined with other infusion base solutions. A sample drug preparation chart for a 70-kg subject is provided in **Table 4** with 200 mg/vials, and 250 mL bags of normal saline as the infusion container. Initiate the infusion within 1 hour of reconstitution and dilution. If the infusion is delayed beyond 1 hour, refrigerate at 2-8C. If refrigerated, allow the diluted solution to come to room temperature prior to administration. If infusion does not begin within 4 hours after reconstitution/dilution, dispose of the original preparation and prepare a new infusion bag by reconstitution and dilution from new vials. Discard any unused portion in the vial. The product does not contain a preservative.

Table 2. Sacituzumab Govitecan Preparation for 10 mg/kg Dosing (Assumes 70-kg Subject).

Total Dose Needed	700 mg (200 mg/vial)
Vials Required	4
Volume of saline to be used for reconstitution	20 mL
Volume after reconstitution of each vial with USP saline	80 mL
Volume Withdrawn for Scheduled Dose	70 mL
Dilute with Normal Saline.	180 mL
Total Volume Dispensed	250 mL
Final Concentration (mg/mL)	2.8

6.3.1 *Sacituzumab Govitecan drug administration*

Subjects will take Sacituzumab Govitecan at their assigned dose on days 1 and 8 in a 21-day cycle. The Schedule of Assessments for the various segments of the study is detailed in Appendix B.

Efficacy of Sacituzumab Govitecan will be determined according to the PCWG2 criteria (Appendix E) and response to Sacituzumab Govitecan will be assessed as the maximum change in PSA from baseline as well as the change in PSA from baseline at the 9-week time point. For subjects who have evaluable and/or measurable metastases, the PCWG2 criteria for response and progression in soft tissue and bone will be used.

6.3.2 *Prophylactic medications*

Pre-medication with acetaminophen, diphenhydramine, corticosteroids, Histamine H2 antagonists (i.e., Pepcid or equivalent) or other drugs is not anticipated; however, it will be employed as clinically indicated to decrease infusion reactions. Subjects with a history of infusional reactions to other antibody therapies or who develop reactions to this study agent may be pre-medicated at the discretion of the treating physician.

6.3.3 *Intravenous administration*

Do not administer as an IV push or bolus. Sacituzumab Govitecan is administered intravenously as a slow infusion as described below.

Intravenous access must be well established prior to initiating infusion. At the time of dosing, the IV line will be connected to an infusion container containing the prepared volume of Sacituzumab Govitecan. Either gravity or an infusion pump may be used. Only normal saline should be used as the infusion base solution, since the Sponsor has not examined the compatibility of Sacituzumab Govitecan with other infusion diluents.

First infusion: Administer infusion over approximately 3 hours. Subjects should be observed during the infusion and for at least 30 minutes following the initial dose for fever, chills or other infusion-related reactions.

Second infusion: Administer infusion over approximately 2 hours if the prior infusion was tolerated. Subjects should be observed during the infusion and for at least 30 minutes after infusion.

Subsequent infusions: Administer infusion over approximately 1-2 hours if prior infusions were tolerated. Subjects should be observed during the infusion.

Following completion, the intravenous line should be flushed slowly with 20 mL normal saline and the end of infusion time recorded. In the event of infusion reactions or vital sign changes, the infusion rate may be slowed, interrupted or terminated, as considered appropriate by the managing physician.

6.3.4 Managing infusion-related reactions

Gilead Sciences, Inc. should be notified within 24 hours of awareness; in the event of any serious infusion reaction.

NCI CTCAE version 4.0 is used to grade all AEs and to provide management guidelines for infusion related reactions.

For a serious infusion reaction considered severe or life threatening (NCI toxicity Grade 3 or higher) an infusion must be permanently terminated.

- Examples of such events include: serious or clinically significant cardiopulmonary events, severe allergic (symptomatic bronchospasm) or anaphylactic reactions, or other severe reactions.
- The occurrence of Grade 3 infusion-related reactions (e.g., Prolonged infusion related reactions-not rapidly responsive to symptomatic medication and/or brief interruption of infusion) also require the infusion to be permanently terminated.

Otherwise, for moderate infusion related toxicity (Grade 2 events), the infusion should be temporarily stopped for at least 15 minutes or until symptoms resolve, and then resumed at the slowed infusion rate, if the subject is stable.

Recommended actions for mild toxicity (Grade 1 events) include slowing the remaining infusion rate.

Any infusion related reaction must have resolved to ≤ Grade 1 prior to a subject receiving the next scheduled infusion.

Table 5 provides a systematic approach to infusion reactions based upon criteria developed by the National Cancer Institute (NCI) for classifying drug toxicity according to increasing levels of severity: mild (Grade 1), moderate (Grade 2), severe (Grade 3) or life-threatening (Grade 4). Management guidelines and examples of qualifying toxicity are also included.

Table 5. Management Guidelines for Infusion Related Reaction

Severity	IV Actions	Medical Support Actions	Examples of Qualifying Events (NCI Toxicity Criteria*)
Mild	Slow remaining infusion rate. Monitor closely for other adverse events.	None required	Transient hypotension; palpitations; mild hypertension; asymptomatic arrhythmias (none requiring treatment); mild allergic reaction (transient rash, drug fever < 38°C), or isolated fever ≤ 39°C; other mild reactions: flushing, rigors, chills, diaphoresis, pruritus, cough, pain, nausea, vomiting, etc.
Moderate	Stop infusion for 15 minutes. Monitor. If stable, resume infusion at slower rate.	For hypotension, IV fluid Replacement. For chills or rigors, pain control, moderate narcotic analgesic (e.g., 25 mg Demerol p.o. or equivalent). For dyspnea, initiate O ₂ , with bronchodilators for subjects with underlying compromised pulmonary function. For general or other allergic reaction, antihistamines (25-50 mg diphenhydramine or equivalent, p.o. or IV, 20 mg Pepcid, p.o. or equivalent) or steroids (50 mg hydrocortisone or equivalent, p.o. or IV)	Infusion-related reaction responding promptly to symptomatic treatment and requiring prophylactic medication ≤ 24 hours; Hypotension requiring fluid replacement; advanced hypertension or symptomatic arrhythmias requiring non-urgent medical attention; moderate allergic reaction (urticaria, dyspnea, drug fever ≥38°C) or isolated fever 39.1 to 40°C; frequent or drenching diaphoresis; controlled intense or widespread pruritus; other moderate reactions: pain, GI, skin, etc.
Severe	Discontinue infusion. Permanently remove from treatment.	If actions above for moderate severity are unsuccessful, initiate emergency resuscitative medications as per institutional protocol (O ₂ , IM or SC epinephrine, IV fluids, bronchodilators, antiarrhythmics, antihypertensives, etc)	Prolonged (not rapidly responsive to symptomatic medication and/or brief interruption of infusion) infusion- related reaction involving recurrence of symptoms after initial improvement; hospitalization indicated for other clinical sequelae; Congestive heart failure/LVEF < 40-20%, hypotension requiring sustained ≥ 24hrs therapy, hypertension requiring more than one drug or arrhythmias symptomatic and incompletely controlled medically or controlled with device, severe allergic reaction (symptomatic bronchospasm requiring parenteral medications, with or without urticaria, allergy-related edema/angioedema and hypotension), rigors/chills unresponsive to narcotics; laryngeal edema with stridor and respiratory distress, other severe pain, GI or skin symptoms, etc.
Life Threatening	Discontinue infusion. Permanently remove from treatment.	Initiate emergency resuscitative medications as per institutional protocol (O ₂ , airway support, IV epinephrine, IV fluids, bronchodilators, antiarrhythmics, antihypertensives, etc)	Infusion-relation reaction which is life-threatening and requiring pressor or ventilator support. Acute myocardial infarction, tamponade, hypertensive crisis, life-threatening arrhythmia (e.g., associated with CHF, hypotension, shock), anaphylaxis, renal failure requiring chronic dialysis or renal transplant, other life-threatening or disabling reactions.

*Partial list of examples. Refer to NCI CTC Version 4.0 for complete list and exact definitions.

[†] Additional medical support as per Investigator judgment.

Additional Medications

Subjects may be medicated during treatment as indicated in the judgment of the treating physician to control potential infusion or hypersensitivity responses. For anaphylactic reactions, appropriate medical measures (e.g., epinephrine, antihistamines, hydrocortisone, and IV fluids) should be taken. Such a subject should not receive additional study drug and should be discontinued from the study.

Nausea, Vomiting and Diarrhea

Gastrointestinal toxicity may be dose limiting with this study agent. Hospital or institutional guidelines may exist and should be consulted for recommended treatment of these conditions in subjects received cancer therapy. Several major oncology organizations have also provided comprehensive guidelines for optimal medical management of nausea, vomiting and diarrhea with cancer treatment. As of this writing, guidelines from these organizations are not stratified by toxicity grade. A partial list of the major medications is provided below, but the hospital/institution guidelines or the references below should be consulted for more detailed information as to management of these conditions. Subjects who exhibit an excessive cholinergic response to Sacituzumab Govitecan treatment (e.g., abdominal cramping, diarrhea, salivation, etc.) can receive appropriate premedication (e.g. Atropine) for subsequent treatments.

Table 6. Recommended Medications for Nausea, Vomiting and Diarrhea

Agent	Dose/Frequency	Route of administration
For Prevention of Acute Emesis:		
Palonosetron	0.075mg	
Decadron	10-20 mg	PO or IV
	10 mg every 12 hours	PO or IV
Granisetron	1 mg or 0.01 mg/kg	IV
	1-2 mg daily	PO
Ondansetron	8 mg or 0.15 mg/kg	IV
	16-24 mg daily	PO
Lorazepam	0.5-2 mg every 4-6 hours	PO or sublingual
Alprazolam	0.5-2 mg every 4-6 hours	PO or sublingual
For Delayed Emesis:		
Aprepitant	125 mg on Day 1 followed by 80 mg on Days 2 & 3	PO
Fosaprepitant	115 mg day 1 only	IV
For Diarrhea:		
Loperamide	4 mg initially followed by 2 mg with every episode for a maximum of 16 mg daily. Discontinue 12 hours after diarrhea resolves and normal diet is resumed.	PO
Octreotide	100-150 mcg three times daily	Subcutaneously
Fluoroquinolones (diarrhea persisting > 24 hrs, ANC < 500 or fever with diarrhea)	(e.g., ciprofloxacin 250-750 mg every 12 hours for 7 days)	PO
Based on NCCN Anti-emesis Guidelines v1.2011; Benson et al (2004) Recommended guidelines for the treatment of cancer treatment-induced diarrhea. J Clin Oncol 22:2918-26; Kris et al (2006) American Society of Clinical Oncology guidelines for anti-emetics in oncology: Update 2006. J Clin Oncol 24:2932-47.		

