6.4.1 Dose reduction and termination guidelines

The most likely toxicities of Sacituzumab Govitecan are expected to be gastrointestinal symptoms and hematologic suppression. All subjects are closely monitored over the course of their treatment. NCI CTCAE v4.0 is used to grade all AEs and to provide the following dose reduction, delay or cessation guidelines in the event of treatment-related toxicity.

In this phase II study, subjects will receive 10 mg/kg Sacituzumab Govitecan once weekly for 2 consecutive weeks followed by 1 week rest in cycles of 21 days, with treatment continued in the absence of progression or unacceptable toxicity. Neutropenia, GI toxicity, fatigue and alopecia were the most common toxicities in phase I testing. All subjects will be closely monitored over the course of their treatment, with NCI CTCAE v4.0 used to grade all AEs and to provide dose reduction, delay or cessation guidelines in the event of toxicity.

On the first treatment day (Cycle 1 Day 1), if a subject experiences ANC $<1000/\mu\text{l}$ or \geq Grade 2 GI toxicity (disease related or from prior treatments), treatment initiation should be withheld until resolved to \leq Grade 1 or baseline level. It is recommended that growth factor support prophylaxis be administered to subjects who receive treatment and whose Cycle 1 Day 1 ANC is $<1500/\mu\text{l}$ and $\geq 1000/\mu\text{l}$.

If recovery to \leq Grade 1 or baseline level requires more than three-week delay, the subject should be withdrawn from the study.

Treatment will be permanently discontinued for a subject in the event of any \geq Grade 3 infusion reactions or for any Grade 2 immediate-type allergic/hypersensitivity infusion reactions (e.g., generalized urticaria, wheezing, hypoxia, dyspnea), which occur after pre-medication with antihistamines, H2 blockers and steroids.

Patients with grade 4 non-hematologic toxicity deemed at least possibly related must permanently discontinue the study drug except for the following situations:

- a. Chloride, bicarbonate, magnesium, phosphate or glucose abnormalities that last <72 hours, if not clinically complicated, and resolve spontaneously or respond to conventional medical interventions
- b. Amylase or lipase elevations that are not associated with symptoms or clinical manifestations of pancreatitis.

Treatment should be permanently discontinued if:

- a. ALT or AST >8x ULN
- b. ALT or AST >5x ULN for more than 2 weeks

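### Section 6.3.4 and Table 5 have staff resume after a Grade 2 infusion reaction and omit the permanent stop that Section 6.4.1 requires for Grade 2 hypersensitivity after premedication

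*Combined protocol and SAP*

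**What the plan says.** Section 6.3.4 sorts infusion reactions by grade. Grade 3 or higher ends the infusion permanently. Below that, "for moderate infusion related toxicity (Grade 2 events), the infusion should be temporarily stopped for at least 15 minutes" or until symptoms settle, and it restarts at a slower rate if the subject is stable. The Moderate row of Table 5 repeats this: "If stable, resume infusion at slower rate". Its qualifying events include "moderate allergic reaction (urticaria, dyspnea, drug fever" and others. Any reaction must have settled to at most "Grade 1 prior to a subject receiving the next scheduled infusion".

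The Severe and Life Threatening rows of Table 5 both add "Permanently remove from treatment". For anaphylaxis, the text after the table says: "Such a subject should not receive additional study drug and should be discontinued from the study".

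Section 6.4.1 sets the termination rules. One sentence permanently discontinues treatment for infusion reactions of Grade 3 or higher and also for "any Grade 2 immediate-type allergic/hypersensitivity infusion reactions (e.g., generalized urticaria, wheezing, hypoxia, dyspnea), which occur after pre-medication" with three drug classes: antihistamines, H2 blockers and steroids.

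On how often that premedication is used, Section 6.3.2 says "Pre-medication with acetaminophen, diphenhydramine, corticosteroids, Histamine H2 antagonists (i.e., Pepcid or equivalent) or other drugs is not anticipated". It goes on to allow it when clinically indicated, including for men who have already reacted to this drug or to another antibody.

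**The concern.** For one type of patient the two sections give different actions. He has had all three premedication classes and then has a Grade 2 immediate-type hypersensitivity reaction. Table 5 has staff pause and restart if he is stable; 6.4.1 says he must not receive the drug again. Section 6.3.4 presents Table 5 as the systematic approach to infusion reactions, so it is the page most likely to be open during one. Staff who work from it alone could restart the infusion in a man whose treatment should have ended.

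The omission looks unintended. The Grade 3 or higher half of the 6.4.1 sentence was carried into Table 5, and the Grade 2 half was not.

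**Working it through.** No arithmetic applies, and the plan has no figure to reproduce. The check sets the instructions side by side.

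| Situation | 6.3.4 text and Table 5 | 6.4.1 | Consistent? |
|---|---|---|---|
| Grade 2 reaction, without the three-class premedication | Pause, resume if stable | No stop rule | Yes |
| Grade 2 reaction after premedication, not immediate-type hypersensitivity | Pause, resume if stable | No stop rule | Yes |
| Grade 2 immediate-type hypersensitivity after all three classes | Pause, resume if stable | Permanent discontinuation | **No** |
| Grade 3 or 4 infusion reaction | End infusion, remove from treatment | Permanent discontinuation | Yes |

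1. *Is the exception stated anywhere in 6.3.4?* There are two Grade 2 instructions, the text and the Moderate row. Neither carries the exception or cites 6.4.1. Of the four Table 5 rows, two (Severe and Life Threatening) state permanent removal.

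2. *Do the two rules cover the same events?* Dyspnea is an example in both. Urticaria is unqualified in Table 5 and generalized in 6.4.1; the unqualified term can include the generalized form, but the match is not word for word. Wheezing and hypoxia, the other 6.4.1 examples, are not named in the Moderate row. Both lists are only illustrative, so the overlap is real but should not be scored as a count of signs.

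3. *Can the situation arise?* Yes. A man has a first Grade 2 allergic reaction and is treated under the Moderate row. The physician premedicates him at the next infusion, as 6.3.2 permits; that section names all three classes. If he reacts again at Grade 2, Table 5 and 6.4.1 diverge.

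4. *How many men?* This cannot be estimated. The protocol gives no rate for Grade 2 hypersensitivity after premedication, and the adverse-event tables in Section 1.3 have no row for infusion reactions or hypersensitivity.

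**Secondary wording.** A later sentence in 6.4.1 requires a permanent stop, whatever the cause, for non-hematologic toxicity described as both life-threatening and Grade 3, with myocardial infarction and stroke as examples. Section 6.3.4 and Table 8 label life-threatening as Grade 4, and Table 5 puts acute myocardial infarction in its Life Threatening row. A separate 6.4.1 sentence stops Grade 4 non-hematologic toxicity only when it is at least possibly related, apart from listed laboratory exceptions. On the Section 7.4.2 scale, Grade 4 non-hematologic events assessed as unrelated or unlikely therefore have no explicit mandatory stop.

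**The case against.** The best reply is that the protocol is workable as it stands. Table 5 is a guideline, and its instruction to resume depends on the subject being stable. The end of Section 6.3.3 lets the managing physician slow, interrupt or end any infusion when a reaction occurs. Section 6.4.1 is the termination section, is worded as mandatory and addresses the specific case, so a site that reads both should apply it. The Severe row also removes men whose reaction is prolonged and recurs after first improving. That leaves mainly Grade 2 reactions that break through premedication, settle and do not return.

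All of this stands, and it keeps the point minor. It does not remove the conflict. Discretion to stop is not an instruction to stop, and a mandatory stop should not depend on staff recalling a sentence in another section during a reaction.

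A reader might infer that 6.3.4 clears such a man for his next infusion once he is back to Grade 1. It does not: recovery is a necessary condition for the next infusion, and nothing there overrides 6.4.1.

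A reader might also infer from the secondary wording that Grade 4 toxicity has no stop rule. That is wrong too. Related Grade 4 non-hematologic toxicity is covered in 6.4.1, subject to its laboratory exceptions, and Grade 4 infusion reactions are covered in both sections. For unrelated events the Table 7 note leaves delay or reduction to the investigator, and Section 5.8 allows removal for any adverse event that the investigator thinks precludes participation. Section 9.4.3 adds safety-committee review of serious events. These are safeguards, but none is an automatic stop.

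**Conclusion.** The conflict is real, narrow and minor. For Grade 2 immediate-type hypersensitivity after the three-class premedication, the guide used during the reaction says resume if stable, while the termination section says stop for good. In the other infusion-reaction situations tabulated above, the two sections agree.

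This assumes that 6.4.1 means all three classes must have been given. If fewer were enough, the group would be wider and the conflict the same. It also assumes that 6.4.1 states the sponsor's intent, which its mandatory wording supports.

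The life-threatening Grade 3 wording is a matter for clarification only. Grade 4 was probably meant to be covered, but the text does not settle it.

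Nothing here bears on the PSA response or 6-month rPFS endpoints, the alpha split or the power. The issue is patient safety and clarity for sites.

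**What to change.** Add one sentence to the Grade 2 text in 6.3.4 and to the Moderate row of Table 5, for example: *Exception: if an immediate-type allergic or hypersensitivity reaction occurs after antihistamine, H2-blocker and steroid premedication, do not resume; discontinue permanently (see 6.4.1).* This needs no new procedure or data. It creates no stop that 6.4.1 does not already require, and it can go into the next amendment.

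Separately, ask the sponsor whether the stop rule that applies regardless of cause was meant to include Grade 4, and have the sentence reworded to match the answer. No single wording follows from the text. Any version that extends the rule to Grade 4 would add some mandatory stops for events assessed as unrelated or unlikely, so the sponsor should make that choice explicitly.
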